6.2 IMPORTANT PROTOCOL DEVIATIONS

A protocol deviation (PD) is important if it affects the rights or safety of the study patients, or if it can potentially influence the primary outcome measurements in a non-negligible way. Important protocol deviations (IPDs) are stored in the DV domain template (Excel spreadsheet). IPDs will be reviewed at Medical Quality Review Meetings (MQRMs) conducted periodically during the trial. A list of PDs will be discussed at the report planning meetings (RPMs).

If the data show other IPDs, this table will be supplemented accordingly at MQRMs or RPMs or through team review of the manual PD log. The final list of IPDs will be confirmed at the

last RPM before DBL. The decision whether a patient will be excluded from the analysis will be made at the final RPM prior to DBL.

Patients with an IPD will be identified and reported in the CTR. In addition, a per protocol set excluding patients with IPDs that could potentially impact the evaluation of the primary endpoint(s) may be defined. Primary endpoint analysis may be performed based on the per protocol set in addition to the treated set.

6.3 SUBJECT SETS ANALYSED

Screened Set (SCS)

This patient set includes all patients who have signed the informed consent. The screened set will be used for patient disposition tables.

Treated set (TS)

This patient set includes all patients enrolled in the trial who were documented to have received at least one dose of ezabenlimab or BI 836880. The TS is used for both efficacy analysis and safety analyses.

MTD set

[figure not shown]
This patient set includes all patients enrolled in dose escalation and confirmation of MTD cohort of the trial (Part 1) who were documented to have received at least one dose of ezabenlimab or BI 836880 and were evaluable for the MTD determination.

Expansion cohort treated set

This patient set includes all patients enrolled in the expansion part (Part 2) and were documented to have received at least one dose of ezabenlimab or BI 836880.

PK analysis set (PKS)

This patient set includes all patients in the TS who provide at least one evaluable observation for at least one PK endpoint and no PK relevant protocol deviation. PKS is used for statistical PK analysis.

6.5 POOLING OF CENTRES

This section is not applicable because centre is not included in the statistical model.

6.6 HANDLING OF MISSING DATA AND OUTLIERS

Missing or incomplete AE dates are imputed according to BI standards (see “Handling of missing and incomplete AE dates”) (3). Missing data and outliers of PK data are handled according to (2). Please refer to Section 7.5 of the CTP for more details. According to (2), missing biomarker data (NOS - no sample, NOR - no valid result, NOA - not analyzed) will not be imputed. Handling of data below or above the limit of quantification, e.g., the myriad panel data:

- BLQ data will be replaced by $\frac{1}{2}$ LLOQ.

- ALQ data will be replaced by ULOQ, if ULOQs are available. Otherwise, ALQ data will be excluded from the analysis.

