7. PLANNED ANALYSIS

For End-Of-Text (EoT) tables, the set of summary statistics includes: N / Mean / SD / Min / Q1 (lower quartile) / Median / Q3 (upper quartile) / Max.

Tabulations of frequencies for categorical data will include all possible categories and will display the number of observations in a category as well as the percentage (%) relative to the respective treatment group (unless otherwise specified, all patients in the respective patient set whether they have non-missing values or not).

Percentages will be rounded to one decimal place. The category missing will be displayed only if there are actually missing values.

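### SAP 6.6 drops above-limit values when no ULOQ is available, which lowers level summaries and pulls changes from baseline toward zero for the analytes concerned (minor)

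*SAP*

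**What the plan says.** SAP Section 6.6 states that "missing biomarker data (NOS - no sample, NOR - no valid result, NOA - not analyzed) will not be imputed". It then gives a rule for results outside the assay range, introduced as "Handling of data below or above the limit of quantification, e.g., the myriad panel data".

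- Low end: "BLQ data will be replaced by" half the LLOQ. No low value is excluded.
- High end: "ALQ data will be replaced by ULOQ, if ULOQs are available. Otherwise, ALQ data will be excluded from the analysis".

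ALQ is not one of the three missing-data codes listed just before. SAP Section 7 says that for end-of-text tables "the set of summary statistics includes: N / Mean / SD / Min / Q1 (lower quartile) / Median / Q3 (upper quartile) / Max". The visible text gives no separate treatment of ALQ results in those summaries, no count of excluded values and no sensitivity analysis.

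**The concern.** An ALQ result carries information: the concentration lies above the range that the assay run could quantify. The SAP accepts this in its main rule, which keeps the value at the ULOQ. The fallback drops that principle only because a number is not to hand, and treats the result like a sample that was never taken. Whether a value is excluded then depends on the value itself, and only at the upper end.

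At stake is the description of any marker for which the fallback is used. Its typical level and spread would look smaller than they are. A pharmacodynamic effect would look weaker, because a patient with an ALQ value at baseline or after it drops out of the paired change. The smaller N would be visible in the tables, but not its cause.

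**Working it through.** **Inputs.** The two rules come from SAP Section 6.6 and the summary statistics from SAP Section 7. The SAP gives no figure for this rule, so there is none to reproduce. It also gives no ALQ share, marker distribution, list of analytes without a ULOQ, or expected direction of any marker. The shares and distributions below are assumptions.

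**1. Levels, normal on the log scale, in SD units.** Let p be the ALQ share and c = Φ⁻¹(1−p), with true mean 0, median 0, SD 1 and Q3 0.674.

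- After exclusion: mean = −φ(c)/(1−p); median = Φ⁻¹((1−p)/2); Q3 = Φ⁻¹(0.75(1−p)); SD = √[1 − cφ(c)/(1−p) − (φ(c)/(1−p))²].
- Kept at the limit: mean = −φ(c) + pc; median = 0 while p < 0.5.

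Example at p = 0.10: c = 1.2816 and φ(c) = 0.1755. The mean after exclusion is −0.1755/0.90 = −0.195. Kept at the limit it is −0.1755 + 0.1282 = −0.047.

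| ALQ share | Mean, excluded | Median, excluded | Q3, excluded | SD, excluded | Mean, at limit | Median, at limit |
|---|---|---|---|---|---|---|
| 2% | −0.049 | −0.025 | 0.628 | 0.95 | −0.007 | 0 |
| 10% | −0.195 | −0.126 | 0.454 | 0.84 | −0.047 | 0 |
| 20% | −0.350 | −0.253 | 0.253 | 0.76 | −0.112 | 0 |

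**2. Levels on the original scale, log-normal with log-SD s.** After exclusion, mean/true mean = Φ(c−s)/(1−p) and median/true median = exp[s·Φ⁻¹((1−p)/2)]. Kept at the limit, mean/true mean = Φ(c−s) + p·exp(sc)/exp(s²/2).

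| ALQ share | s | Mean, excluded | Median, excluded | Mean, at limit |
|---|---|---|---|---|
| 2% | 0.5 | −4.1% | −1.2% | −1.1% |
| 10% | 0.5 | −13.0% | −6.1% | −5.0% |
| 20% | 0.5 | −20.8% | −11.9% | −9.7% |
| 2% | 1.0 | −12.9% | −2.5% | −5.1% |
| 10% | 1.0 | −32.1% | −11.8% | −17.1% |
| 20% | 1.0 | −45.4% | −22.4% | −28.1% |

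**3. Mean change from baseline, log scale.** Simulation of 2,000,000 baseline/post pairs, SD 1 at each time, limit at the 90th percentile of baseline. Under exclusion, a pair is dropped if either value is ALQ.

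| True change | Excluded, corr. 0.5 | At limit, corr. 0.5 | Excluded, corr. 0.8 | At limit, corr. 0.8 |
|---|---|---|---|---|
| +1.0 | +0.75 | +0.77 | +0.88 | +0.77 |
| +0.5 | +0.40 | +0.42 | +0.45 | +0.42 |
| 0 | 0.00 | 0.00 | 0.00 | 0.00 |
| −0.5 | −0.44 | −0.47 | −0.47 | −0.47 |
| −1.0 | −0.91 | −0.96 | −0.96 | −0.96 |

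Exclusion shrinks the change in both directions and leaves a null change alone. Keeping values at the limit does not cure this. At correlation 0.5 it is slightly better than exclusion, and at 0.8 with a rising marker it is worse (+0.77 against +0.88). What it does preserve is the median at each visit, and so the difference between visit medians, while fewer than half the values at each visit are ALQ. In these runs the largest ALQ share at any visit was 39%.

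**The case against.** The strongest case against is about reach. The main rule already keeps ALQ values at the ULOQ, and exclusion is only a fallback. The SAP does not say that any analyte lacks a ULOQ, and if none does, the rule never operates. The visible primary endpoints (DLTs, objective response) and secondary endpoints (adverse events, disease control, duration of response, PFS, tumour shrinkage, PK parameters) are not shown to depend on it. Missing PK data and outliers are referred to a separate standard. Biomarker endpoints and methods may sit in text that is not public, so the absence of visible ALQ counts or rank-based methods is no omission. All of this stands, and it keeps the point minor.

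Three stronger readings are tempting, and the SAP supports none of them.

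- A reader might infer that changes from baseline are always biased downward. They are pulled toward zero, so for a falling marker the bias is upward. The SAP does not say which way any marker moves.
- A reader might infer a large bias from ALQ shares of 10% or more. The SAP gives no share, and at 2% the shift in the log-scale mean is only about −0.05 SD.
- A reader might infer that a real association between marker and outcome will be hidden. No such analysis appears in the visible text.

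It is also fair to object that an ALQ value is known to exceed the quantified values only within one assay run with one range and dilution. The highest quantified value is therefore an imperfect substitute. It can lie well below the true limit in a small run, and it does not exist if every value in the run is ALQ. That limits the choice of remedy but does not justify exclusion.

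**Conclusion.** The point holds in narrow form. For any analyte with ALQ results and no ULOQ, following Section 6.6 as written excludes observed high values while low values are kept. The downward direction for the mean, median, Q3 and maximum does not depend on the assumed distribution. The sizes do, and so does the fall in SD, which is shown here for a normal (log) scale. Across assumed ALQ shares of 2% to 20%, the mean falls by about 0.05 to 0.35 SD and the median by about 0.03 to 0.25 SD. Changes are attenuated in either direction, by an amount that depends on the shift, the correlation and where the limit lies. No dose, efficacy or safety conclusion is shown to be at risk. This is a minor correction to a stated rule for supportive data.

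**What to change.** Replace the exclusion sentence in Section 6.6. Where no ULOQ is available, ALQ values should stay in the analysis as right-censored or top-ranked, for example set to the highest quantified value of that analyte in the same assay run, and be flagged. Where no usable quantified value exists in the run, keep them as top-ranked or censored without a substituted number. For these analytes, base interpretation on medians or ranks and report the number of ALQ values per analyte and visit. For changes, compare visit medians or treat the change as censored; a mean of substituted differences should not be relied on.

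The cost is one sentence in the SAP, one programming rule and a count column. A small underestimate of the mean level remains (about −0.01 to −0.11 SD for ALQ shares of 2% to 20% if values sit at the limit, somewhat more if the highest quantified value lies below it). Substitution alone does not remove the attenuation of mean changes.

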6.7 BASELINE, TIME WINDOWS AND CALCULATED VISITS

Visit labels

Study days and visits will be labelled according to the flow charts in the CTP. The visit schedule with accompanying details can also be found in the flow charts in the CTP.

Definition of “baseline”

For laboratory values, the baseline value is the most recently observed value before or on the first day of infusion of trial medication; for laboratory measurements, the examination time may also need to be considered, in instances where time is recorded in addition to date. For all other data values, baseline is defined as the most recent measurement taken prior to first administration of trial medication. If not available, then the values reported at the screening visit will be considered.

Time windows

Time windows and visits will be calculated to determine the planned day of tumour measurement and response status based on the protocol-specified tumour imaging schedule. Imaging data will be displayed as: Screening, Week 6, Week 12, Week 18, etc. The number of weeks will be calculated using their relative day (from start of treatment) using a ±3 week window. (Images taken in the first 3 weeks from start of treatment will be assigned to Week 6.) Images which are not older than 28 days at start of treatment will be sufficient as screening images and do not need to be repeated.

How to include measurements taken between time windows

The same visit windows will be used for safety laboratory and vital sign assessments. If there are multiple safety or laboratory values in one time window on treatment, the worst value will be selected for the by-visit analyses.

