7.8.2 Laboratory data

The analyses of laboratory data will be descriptive in nature and will be based on BI standards “Display and Analysis of Laboratory Data” (7). CTC grade for applicable lab parameters will be calculated according to CTCAE v5.0 (6).

Descriptive statistics of all converted laboratory values by visit will be provided including changes from baseline. Frequency tables of transitions relative to the reference range and of possible clinically significant abnormalities will be produced. For those parameters that have CTC grading possible clinically significant abnormalities are defined as those laboratory values with a CTC grade ≥ 2 that have had an increase of ≥ 1 grade from baseline. For those parameters for which no CTC grade has been defined standard BI project definitions will be used to decide on clinical significance. Further frequency table will show the transition of CTC grade from baseline to worst value and from baseline to last value on treatment.

Summaries will be produced of laboratory data recorded prior to treatment, on-treatment and post-treatment. For details on the treatment definition, see [Section 6.1](#).

The focus of the laboratory data analysis will be on the following laboratory parameters:

[figure not shown]
- Low values: Activated Partial Thromboplastin Time (aPTT), Prothrombin Time (PT), International Normalised Ratio (INR), White Blood Cell Count (WBC) with differential, Platelets (PLT)
- High values: Aspartate Aminotransferase (AST), Alanine Aminotransferase (ALT), bilirubin, Alkaline Phosphatase (AP), Activated Partial Thromboplastin Time (aPTT), Prothrombin Time (PT), International Normalised Ratio (INR), Protein levels in urine

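### By-visit laboratory summaries take the worst value in ±3-week imaging windows against a single-value baseline, so means drift toward worsening with no true change

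*SAP*

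**What the plan says.** Section 6.7 derives its time windows from the imaging schedule, with nominal times at Week 6, 12, 18 and so on: "The number of weeks will be calculated using their relative day (from start of treatment) using a ±3 week window". For the start of treatment it adds: "Images taken in the first 3 weeks from start of treatment will be assigned to Week 6". It then extends the scheme to safety data: "The same visit windows will be used for safety laboratory and vital sign assessments". Where a window holds several values, the rule is: "If there are multiple safety or laboratory values in one time window on treatment, the worst value will be selected for the by-visit analyses".

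Baseline follows a different rule. In the same section: "For laboratory values, the baseline value is the most recently observed value before or on the first day of infusion of trial medication". That is one reading, not the worst of several.

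The output affected is in Section 7.8.2: "Descriptive statistics of all converted laboratory values by visit will be provided including changes from baseline". Section 7 lists the mean, SD, quartiles and range as the standard summary statistics. Section 7.8.2 also plans tables for which a worst value is the natural input: "Further frequency table will show the transition of CTC grade from baseline to worst value and from baseline to last value on treatment", together with tables of possible clinically significant abnormalities.

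Two other statements bear on the point. Section 6.7 opens with "Study days and visits will be labelled according to the flow charts in the CTP", and Section 6.1 gives a three-weekly dosing interval.

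**The concern.** A change from baseline is interpretable when both ends are measured in the same way. Here the baseline end is one reading, and the on-treatment end is the most extreme of however many readings fall in a six-week window. The worst of several readings is on average worse than one reading even if the patient has not changed. The size of this artefact depends on how many readings the window holds, which has nothing to do with the drug.

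By-visit means and changes for laboratory parameters would therefore mix any true effect with a selection effect. If the number of readings differs between windows, the artefact differs too, and the time course can show a rise and fall that is not there. Six-week windows also merge adjacent three-week cycles, so the by-visit tables lose the resolution of the dosing schedule.

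**Working it through.** The SAP states no figure on this point, so there is none to reproduce. The check asks how large the by-visit change would be if nothing truly changed.

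**Inputs from the SAP**
- Windows of ±3 weeks around Week 6, 12, 18 and so on, each six weeks wide (Section 6.7).
- Worst value per window; a single baseline value (Section 6.7).
- Three-weekly dosing (Section 6.1).

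**Assumptions**
- Samples are taken at each dosing visit, so k = 6/3 = 2 readings per window. The sampling schedule is in the protocol, which is not shown.
- Readings vary around a constant patient level with a common within-patient SD. Results are in units of that SD, with higher taken as worse. For parameters where low is worse the sign reverses.

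**Step 1: independent readings.** The expected change from baseline is the expected maximum of k standard normal values, E[max_k] = ∫ x·k·φ(x)·Φ(x)^(k−1) dx. The chance that the worst of k is worse than baseline is k/(k+1).

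| k | Expected shift (SD) | Chance of appearing worse |
|---|---|---|
| 1 | 0 | 50% |
| 2 | 0.56 | 67% |
| 3 | 0.85 | 75% |
| 4 | 1.03 | 80% |
| 5 | 1.16 | 83% |
| 6 | 1.27 | 86% |
| 7 | 1.35 | 88% |

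For k = 2 the integral has the closed form 1/√π = 0.564.

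**Step 2: correlated readings.** With first-order autoregressive correlation ρ, the k = 2 shift is √((1−ρ)/π).
- ρ = 0.3: √(0.7/π) = 0.47 SD.
- ρ = 0.5: √(0.5/π) = 0.40 SD.

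By simulation, k = 3 gives 0.75 and 0.64 SD at the same correlations. Correlation shrinks the shift but does not remove it.

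**Step 3: the first window.** If the rule for images from the first 3 weeks also applies to safety data, the Week 6 window spans about Weeks 0 to 9, against six weeks for later windows. Later windows hold k = 2 (0.56 SD) under each schedule below. The ranges for k reflect whether the lower or upper window edge is included, which the SAP does not state.

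| Assumed sampling | k at Week 6 | Shift at Week 6 (SD) | Excess over later windows (SD) |
|---|---|---|---|
| Three-weekly | 2 or 3 | 0.56 or 0.85 | 0 or 0.28 |
| Plus weekly in cycle 1 | 4 or 5 | 1.03 or 1.16 | 0.47 or 0.60 |
| Plus weekly in cycles 1 and 2 | 6 or 7 | 1.27 or 1.35 | 0.70 or 0.79 |

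If the rule does not carry over, the first two schedules give k = 2 throughout and no peak. The third gives k = 4 at Week 6 and an excess of 0.47 SD.

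**Step 4: after the change.** With one value per visit, k = 1. The expected shift is 0 and the chance of appearing worse is 50% at every visit.

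**The case against.** The strongest defence is that taking the worst value per window is a recognised, conservative safety convention and that these analyses are descriptive. Both are true. The convention suits shift and abnormality tables, where the question is how bad things became. It does not suit a mean change by visit, where the question is what happened at that time.

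Several stronger readings are tempting, and the SAP does not support them.

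- **A false early peak is certain.** The rule for the first 3 weeks is worded for images only, the window edges are not defined, and the safety sampling schedule is not shown. Some plausible combinations give no peak.
- **Mean blood pressure will appear to rise by a given number of mmHg.** Section 7.8.3 names a shift table for blood pressure and no by-visit table of mean changes. No within-patient SD is given either. A by-visit vital-sign summary, if produced, would drift in the same way.
- **Cycle 1 toxicity is hidden.** Dose-limiting toxicities are assessed in the first cycle (Section 5.1), and Section 7.8.1 plans a first-cycle adverse-event analysis for Part 1. Only the by-visit summaries lose cycle resolution.
- **The visit labels contradict the windows.** Labelling visits by the flow charts and assigning values to analysis windows can coexist. The text only leaves open which of them the safety tables display.
- **The direction of worst is undefined for aPTT, PT and INR.** Section 7.8.2 lists them under both low and high values, so one worst value is ambiguous. The sponsor's laboratory standard, which the SAP cites, may settle this.
- **The day-1 baseline value is counted again as on-treatment.** The selection rule is limited to on-treatment values, and Section 6.7 allows for examination time. At most an ambiguity remains for untimed day-1 samples.

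**Conclusion.** The point holds for by-visit laboratory summaries. It follows from rules that the SAP states, not from detail left to the protocol. Followed as written, they move by-visit means and changes from baseline toward worsening by about 0.4 to 0.6 within-patient SD when a window holds two readings. Three independent readings give 0.85 SD. The two-reading figure rests on sampling at each three-weekly dosing visit.

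Loss of cycle 1 in these summaries, and an early peak of 0 to about 0.8 SD, are conditional. They depend on how the rule for early images is applied and on the protocol's sampling schedule. No hypothesis test, sample size or primary endpoint is touched. The harm is to the reading of the laboratory time course, and the change is worth making before programming.

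**What to change.** In Section 6.7:

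1. Limit the ±3-week windows, including the rule for the first 3 weeks, to imaging.
2. Summarise laboratory and vital-sign data at the protocol flow-chart visits, using the scheduled value or the one nearest the planned day.
3. Keep the worst value, including unscheduled values, for the baseline-to-worst shift tables and the abnormality tables.
4. Show low and high directions separately for aPTT, PT and INR.

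The cost is SAP wording, a second visit-window map in programming and more rows in the by-visit tables. No safety information is lost, because the worst values remain in the tables that Section 7.8.2 already plans.

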7. PLANNED ANALYSIS

For End-Of-Text (EoT) tables, the set of summary statistics includes: N / Mean / SD / Min / Q1 (lower quartile) / Median / Q3 (upper quartile) / Max.

Tabulations of frequencies for categorical data will include all possible categories and will display the number of observations in a category as well as the percentage (%) relative to the respective treatment group (unless otherwise specified, all patients in the respective patient set whether they have non-missing values or not).

Percentages will be rounded to one decimal place. The category missing will be displayed only if there are actually missing values.

